	Staff costs to Victim Support	Time costs of other Victim Support staff (e.g. triage officers, management team, governance board) on activities related to WeMatter (e.g. undertaking community engagement and promotion activities, handling referrals, arranging and completing triage calls, completing admin tasks, data monitoring and reporting, providing staff support and training, completing case reviews and service audits, conducting victim and stakeholder involvement activities, managing the WeMatter Youth Advisory Board, etc.)	Victim Support
	Facilities, equipment and materials costs to Victim Support	Expenses incurred by Victim Support on WeMatter related activities	Victim Support
	Facilities, equipment and materials costs to Victim Support	Funds from Victim Support to help CYP get digital access to WeMatter	Victim Support
	Costs to wider society (quantifiable but unmonetisable)	Time of CYP on WeMatter related activities	Interviews with CYP Interviews with parents/carers

			Interviews with facilitators
	Costs to wider society (presented separately as units of time)	Time costs of parents/carers on WeMatter related activities	Interviews with CYP Interviews with parents/carers
	Costs to wider society	Expenses incurred by CYP and their families on WeMatter related activities	Interviews with CYP Interviews with parents/carers
	Costs to other public services	Time costs of staff at schools, community centres, and referrers on WeMatter related activities	Interviews with parents/carers Interviews with facilitators Interviews with representatives from LA and referral agency
	Costs to other public services	Expenses incurred by schools, community centres, and referrers on WeMatter related activities	Interviews with facilitators Interviews with representatives from LA and referral agency
Prerequisites (listed and valued but not included in the cost estimates)	Other intervention costs to Victim Support	Licence to use the Rock Pool CYP Domestic Abuse Recovery Toolkit	N/A
	Staff costs to Victim Support Costs to other public services	Existing referral pathways	N/A
	Costs to other public services Costs to wider society	Existing access to IT equipment and Zoom	N/A

Start-up costs	Staff costs to Victim Support	Assessing demand and other preparation work before introducing WeMatter to a new local authority	Victim Support
	Staff costs to Victim Support Costs to other public services	Introducing WeMatter to the established referral pathways and setting up new referral pathways where required	Victim Support
	Staff costs to Victim Support	Administrative costs associated with hiring and training new staff	Victim Support
	Staff costs to Victim Support Facilities, equipment and materials costs to Victim Support	Setting up the required operational infrastructure and procedures	Victim Support

Ethics & participation

Verian is the independent evaluator for this research, and as such is responsible for securing ethical approval. During the project planning and design phases, we followed Verian's internal research ethics review process to ensure the proposed project approach met ethical standards and represented a balanced and responsible approach to achieve the aims of this evaluation. The ethics panel selected for this project consisted of three Directors all external to the project team and to Verian's Behavioural Practice team. Their entire role on this project is to ensure it meets the organisation's high ethical standards.

Potential harms associated with this project will be considered and embedded in Verian's safeguarding approach. The relevant considerations and risks will also be written into the ethical approval process.

Participants' parents/carers will be provided information in writing on their right to withdraw from the trial, in the form of a Parent Information Sheet and a project Privacy Notice. The Privacy Notice will detail what data Verian process, how Verian does so, the legal basis and purpose(s) for processing data, and participants' rights. The document will also provide contact information to raise concerns, exercise their rights, or escalate issues if needed. It will also inform participants that we will disclose to authorities if they say anything that raises concern about their safety or wellbeing. See Figure 1 for the detailed flow of the consent process.

The recruitment materials the ethics panel reviewed and signed off were:

- The Evaluation Protocol
- The triage call and follow-up consent call scripts
- The Participant Information Sheet.

Ethics clearance and input regarding these materials and the overall trial was granted by Verian's internal Research Ethics Committee on 28 May 2024. The ethics reference is VERIAN REC (24/BO01/04).

Participant consent

As described in more detail in [section 3](#), in the subsection 'Referral, eligibility, and consent', this project relies on the parent/carer of a CYP referred for WeMatter to actively consent and opt into participating in the evaluation of the WeMatter service. The parent/carer of the CYP will be given the opportunity for their child to participate in the service and its evaluation during the initial triage call with Victim Support and will be informed that participating in the service is conditional on participating in the evaluation. Following the initial triage call, the parents/carer will receive a Participant Information Sheet and Privacy Notice that provides further detail about the evaluation and how their data will be handled. The parents/carers will then have a follow-up call with the WeMatter facilitator assigned to their child to seek their informed oral consent.

Participants who are not eligible for WeMatter or whose parents/carers do not consent to participate in the evaluation will be passed back to the referrer or will be signposted/referred to/advised on alternative provision following Victim Support's standard processes. Parents/carers

of CYP participating in the evaluation may also withdraw their consent to be part of the evaluation at any time by informing Victim Support and/or Verian. If this happens after the follow-up call and randomisation, the CYP will continue to receive WeMatter as planned but their data will not be shared with Verian. See Figure 1 for the visualisation of the consent process.

Approach to ensuring confidentiality

Our data protocols and data security procedures are designed to minimise the risk of data loss and data breaches and protect respondents' confidentiality. We have well-established policies and procedures in place to transfer, store, process, analyse, and dispose of data securely in line with the 2018 Data Protection Act and UK GDPR requirements. We are certified to ISO 27001 and hold a valid Cyber Essentials certificate.

Safeguarding approach

Verian's Senior Safeguarding Committee (SSC) has overall responsibility for safeguarding policy and compliance.

Verian field interviewers may, through their work, observe or encounter safeguarding concerns or have these disclosed to them, they must follow the procedure set out in this policy to recognise, respond to, report and adequately record those concerns. The Head of UK Data & Operations will be responsible for ensuring compliance of this policy by field interviewers. Verian interviewers and contractors are to follow the procedure as set out in this policy, and the Project Director for the project is responsible for compliance and escalation.

In the context of the WeMatter evaluation, we will include all participants (including those who turn 18 during the intervention period) as children from a safeguarding perspective. In the context of child protection, children and young people refers to anyone under 18 years of age. The Market Research Society (MRS) Code of Conduct defines a 'child' to be under 16, 'young people' as those aged 16 and 17, and an 'adult' as 18 and over. As signatories to the Convention of the Rights of the Child (UNCRC), the UK has an obligation under law to protect children from all forms of violence, abuse and harm. Whilst we recognise that Verian is bound by MRS' Code of Conduct for how we approach and uphold consent standards in research for the purposes of safeguarding children, we must disclose any concern we have around risk of harm for those under the age of 18. Whilst those aged between 16 and 18 have the right to consent to taking part in the research, for this project we are seeking consent from parents/carers for all participants as agreed with Foundations and Victim Support. Please note that it is Verian practice to escalate all cases where we have a concern without or without consent if the person is under 18.

If a field researcher becomes concerned about the safety or wellbeing of a participant meeting the definition of requiring safeguarding as above, they are to:

- If the concern is a threat to life or significant threat to the participant's immediate health or wellbeing, call the relevant emergency services (Police, Ambulance, Fire).
- Ask the participant if the participant is OK.
- Ascertain if the field researcher knows how to help themselves (where possible).

- Inform the participant (or the parent, if the participant is a CYP and the concern does not seem caused or exacerbated by the parent) that they have become concerned about their safety or wellbeing, and immediately end the interview (and recording) and consider the participant fully withdrawn from the research process.
- Provide information relating to help that may be available to the participant (e.g. support organisations) or their parent.
- Ensure as far as is possible that the participant receives promised incentive before they leave.
- As soon as possible (within 24 hours), inform the project safeguarding lead ([name]) responsible for providing support to the end user about the expressed concern. Researchers are not to reveal any unnecessary details about the content of the interview.
- If they have cause for concern that the participant is at risk of harms, complete the safeguarding escalation template (within 24 hours). Share the completed template with the project safeguarding lead ([name]) and the Verian Chief Safeguarding Officer (CSO).
- The CSO will assess the case (including information provided to help ascertain if the participant can help themselves). The CSO will contact Victim Support and Foundations to outline that there has been a safeguarding event and that Verian has taken appropriate action.
- Record the incident in the project incident log and review, jointly with [name], if any research materials or processes need to be amended to prevent further incidents.

Registration

The trial was preregistered with, and the evaluation protocol uploaded to, the Open Science Framework (OSF) on 20/06/2024. The OSF registration of the project, and the Evaluation Protocol as uploaded, can be found here: <https://osf.io/mbp49/>.

Data protection

Verian (trading as Verian Group UK Ltd.) will serve as data processor for the data used for the project evaluation, with Foundations as data controller for this data (jointly with Victim Support). Any personal data shared with Verian will be pseudonymised by replacing names/contact details with a unique ID.

Verian is registered with the Information Commissioner's Office for all our research and other activities, holding ISO27001 accreditation which certifies the legal, physical, and technical controls involved in our information risk management process. We also hold the Cyber Essentials Certificate, and abide by the Data Protection Act 2018, and embed Data Protection by design in all our work. We have a GDPR champion and Quality and Information Security team who consult on all data privacy issues.

Data protection laws require us to meet certain conditions before we are allowed to use data in the manner described in this notice, including having a lawful basis for the processing.

For all information collected for this project Verian is relying on the lawful basis of LEGITIMATE INTERESTS, as instructed by the data controller, Foundations.

Verian's lawful basis for processing CYP's, and WeMatter facilitators' personal data is legitimate interests (as per Article 6 (1) (f) of the UK GDPR) and we have considered that your interests and fundamental rights do not override those legitimate interests). It is necessary in Verian's 'legitimate interests' to process the personal data identified above in order to deliver a meaningful randomised controlled trial (RCT) that has been commissioned by Foundations and the Evaluation Accelerator Fund.

We will process special category data related to health in the form of disability and additional needs (SEN), public care status, sexual orientation, ethnicity and gender identity We will collect this data to provide descriptive statistics about the sample for this project to Foundations, as individuals with disability and additional needs and public care status are likely to be especially vulnerable and it is therefore imperative to understand their role and presence in this evaluation. For the processing of this special category data Verian is also relying on LEGITIMATE INTERESTS.

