Secondary outcome	Variable	N/A We will consider adding secondary outcome(s) based on facilitator and CYP feedback about the demands of the data collection. Secondary outcomes we could consider adding later are self-esteem or 'feeling of being supported'.
	measure (instrument, scale)	TBC

Figure 1: Illustration of trial process

Referral, eligibility, and consent

Referrals into Victim Support are managed by a triage team, members of which contact the safe parent/carer of the referred CYP for an initial triage call. The triage team will provide information about the service and a short summary of its evaluation and will enquire about the CYP's needs and parents'/carers' potential consent to participate in the WeMatter service and its evaluation during the initial triage call. They will be informed that participation in the service is conditional on participation in its evaluation. At this stage, if parents/carers don't want their child to participate in WeMatter or the evaluation, Victim Support will signpost them to an alternative service or re-refer them to their original referrer.

Before parents/carers can consent to the service and its evaluation, they will need to read the Participant Information Sheet and Privacy Notice that detail the evaluation, its purpose and the associated data sharing arrangements and agreements. These will clearly inform the parent/carer that they are able to opt out of the evaluation at any point, with CYP receiving the same information before they can assent during their first one-to-one meeting with their facilitator. The documents will be sent to the parents/carers via email or text message following the initial triage call. The triage team will arrange a follow-up call between the service facilitator assigned to their child and the parent/carer to seek their informed oral consent. During the follow-up call, the facilitator will confirm that the parent/carer has read and understood all of the written materials and record their oral consent. Once their consent is confirmed the facilitator will randomly allocate their child to a pre-randomised group and inform them of the randomisation outcome.

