To ensure participants are engaged with the service, Victim Support need to be able to tell parents/carers during the follow-up consent call which service their child will receive, and when this will start. This means the outcomes of the randomisation need to be known to the facilitator during the call, as this is when eligibility for WeMatter is confirmed. To allow for this, we will provide the WeMatter facilitators with a pre-generated list for each ‘type’ of group they run (three age cohorts, each either at home or in school) to which every new referral will be added *in order of referral*. When the facilitator has taken consent and added the CYP’s details to the list, they will be able to see if the CYP is in the intervention or the control group.

To generate this list for each block of 20, we will number the order of referral chronologically, from 1st (earliest) to 20th (last). We will randomly sample 10 positions to be assigned to the intervention group. However, given that we expect most blocks to include 16 CYP, we need to separately sample 8 and 2 positions within ‘sub-blocks’ of 16 and 4 to keep balanced group sizes in case the remaining 4 positions do not get filled. We will use the *sample* function in the *base* package within the R statistical programming software to randomly select eight and then another two positions in each block to be assigned to the intervention group. The random number seeds (i.e. the starting numbers used for the pseudorandom number generator) will be different for each block, with each

seed number equal to the block number. In this way, we can replicate the results of (pseudo)randomisation.

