Victim Support will conduct quality checks to confirm that CYP are assigned to their respective block (age cohort and delivery setting) in chronological order of referral. This means the date of consent for the first CYP in each block should be the earliest date, and so on. The facilitators will not be blinded to the randomisation outcome, but they will be asked not to look at the randomisation allocation until after consent to participate in the trial has been granted. They will also be instructed not to influence or reveal the outcome of randomisation before the parent has consented to their child being part of the trial and the child has been assigned to a block. Once consent has been granted, facilitators can communicate the outcome of the randomisation (i.e. whether the CYP will be in the treatment or control group) to the parent, but they cannot alter the allocation at this stage. If parents/carers are unhappy about their allocation, they may choose to opt out of (or withdraw from) the trial but they cannot be provided another allocation. Training for the facilitators on the allocation process will emphasise the importance of ensuring fidelity to the randomised allocation process for the trial.

Due to the evaluation being a pilot, the evaluators will not be blinded to the outcomes of randomisation, regardless of the randomisation approach used as this will also help to inform our assessment of the design for the rapid design testing aspect of the trial.

Participants

Victim Support had originally envisaged conducting the trial in four areas. They have since expanded the scope of the areas where the trial will recruit participants from to ensure demand for services during the trial. The CYP will be recruited for the randomised trial from referrals to Victim Support and partners from all areas in England.

The trial will include children and young people who:

- Have been referred to Victim Support and witnessed or directly experienced domestic abuse, but no longer experience it and no longer live with the alleged perpetrator of the abuse.
- Are between the ages of 8 and 17 years old at the time of referral.
- Are residing in participating local authorities, i.e. all areas in England.
- Speak proficient English to participate.

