- [name]: IPE Project Manager
- [name]: Impact Evaluation Manager
- [name]: Executive Support
- [name]: Expert Advisor
- [name]: Expert Advisor
- [name]: Expert Advisor
- [name]: Lived Experience Expert
- [name]: Lived Experience Expert

Timeline

Dates	Activity	Staff responsible/ Leading
20/06/2024	Foundations sign off the final version of the evaluation protocol with ethics approval obtained from Verian's ethics panel.	[name]
03/06/2024	Victim Support start processing referrals for the trial, i.e. recruitment and randomisation for the trial starts .	[name]
20/06/2024	Evaluation protocol published on Foundations website and the Open Science Framework (OSF).	[name]
17/06/2024	First cohort of WeMatter groups in the trial start.	[name]
July 2024	
First evaluation progress review meeting with Foundations and Victim Support. This meeting will consider:
 
 1. If there is capacity to increase the data collection requirements to include secondary outcome measure (or to do so for older cohort(s))? And, if there is capacity, which secondary outcome(s) should be collected? 2. Who should administer the outcome assessments, 'familiar' or 'unfamiliar' facilitators? 	[name]
September	Mid-project evaluation in-depth review meeting with Foundations and Victim Support.	[name]
Late-September 2024	Recruitment into the trial stops. The last scheduled paired Treatment/Control cohort commences early October, to allow recruited participants in the Control group to complete a 10-12 week waiting period and then a 10-week	[name]

	WeMatter programme, with data collection at the end of the programme completed by 31 March 2025.	
December 2024	Final data collection for impact evaluation.	[name]
31/03/2025	Interim evaluation report completed.	[name]
31/03/2025	WeMatter delivery completes (final Control groups have received WeMatter).	[name]
08/09/2025	Final evaluation report completed.	[name]
12/09/2025	Analysis code and pseudonymised data published on GitHub and Foundations' data archive.	[name]

References

- Angrist, J. D., Imbens, G. W. & Rubin, D. B. (1996). Identification of causal effects using instrumental variables. *Journal of the American Statistical Association*. 91 (434), 444–455. <https://doi.org/10.1080/01621459.1996.10476902>

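### Allocation is not reliably concealed: the facilitator who takes consent also holds the pre-generated list, and the order check mixes referral order with consent order

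*Protocol*

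**What the plan says.** **Consent and allocation** (Protocol, section 3, Referral, eligibility, and consent). The facilitator assigned to a child makes the follow-up call and records the parent's oral consent. "Once their consent is confirmed the facilitator will randomly allocate their child to a pre-randomised group" and tells the parent the result. If the parent is unsure, the facilitator asks to set up a further call.

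**The list** (Randomisation). "we will provide the WeMatter facilitators with a pre-generated list" for each type of group: three age bands, each at home or in school. The reason given is that parents must hear the arm and start date on the phone, so the facilitator has to learn the result in that call, where eligibility is also settled. Once consent is taken and the child is entered, "they will be able to see if the CYP is in the intervention or the control group". Each block has 8 intervention places drawn from the first 16 and 2 from the last 4, using R's sample function, with "seed number equal to the block number".

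**Safeguards** (Randomisation). Facilitators are not blinded, but "they will be asked not to look at the randomisation allocation until after consent". They are trained, told not to influence or disclose the result beforehand, and cannot change an allocation after consent. Children are listed by order of referral. The delivery organisation checks this order, but the check is spelled out in terms of consent: "This means the date of consent for the first CYP in each block should be the earliest date".

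**Dates.** Recruitment starts on 3 June 2024 and stops in late September 2024 (Timeline). The protocol was made public on 20/06/2024 (Registration, Timeline).

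**The concern.** If the person obtaining consent can know the next arm, then who is consented, and when, can come to depend on that arm. The comparison would then carry selection bias.

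Three features of this trial raise the stakes:

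- The recruiting staff also deliver the service and administer the outcome scale.
- The Week 1 score, the main covariate, is collected after the arm has been disclosed. Adjusting for it cannot remove selection on unmeasured factors.
- The effects sought are small: the Sample size/MDES section gives 0.11 to 0.21 standard deviations.

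The protocol discusses bias from unblinded assessors under Primary outcomes. It does not discuss selection through foreknown allocation.

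**Working it through.** **1. The plan's own figures.** 47 blocks × 16 = 752 children and 47 × 8 = 376 per arm, as stated. The point does not affect sample size or MDES.

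**2. Is the list concealed?** Set the statements side by side. The facilitator holds the list, confirms eligibility in the call, takes consent and makes the entry. The arm is meant to become visible after entry, but no mechanism for this is given. Asking facilitators not to look makes sense only if they could look. The ban on changing an allocation applies after consent, whereas selection would occur before it.

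**3. Does the order check work?** Suppose A is referred before B, and the next two places are control, then intervention (an illustration, not a figure from the protocol).

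- *Places follow consent.* If A's call is completed after B's, B takes the control place and A the intervention place. The consent dates run in perfect order, so the check passes whether or not the delay was deliberate.
- *Places follow referral.* A keeps the control place. If A's parent asks for a second call, which the protocol allows, B consents first. The dates are then out of order and the check fails although nothing improper happened.

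The check can expose skipped places. It cannot reliably expose selective timing of consent.

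**4. The seed.** Without knowledge of the seed, a 16+4 block has C(16,8) × C(4,2) = 12,870 × 6 = 77,220 possible sequences. With a published rule that sets the seed to the block number, the candidates collapse to very few. Two codings of the rule in R 4.3.3 gave the same sequence for each of blocks 1 to 3. This shows that regeneration is feasible, not that these are the trial's lists. The exposure outside the team begins on 20 June, 17 days after recruitment starts on 3 June.

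**5. Predictability from the fixed sub-blocks alone.** Take a permuted block of 2m places and someone who sees every past allocation and always guesses the arm with more places left.

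- Expected correct guesses = m + (2^(2m)/C(2m,m) − 1)/2
- Expected fully determined places at the end = 2m/(m+1)

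| Sub-block | Correct guesses | Share | Determined places |
|---|---|---|---|
| 16 (m = 8) | 8 + (65,536/12,870 − 1)/2 = 10.05 | 62.8% | 16/9 = 1.78 |
| 4 (m = 2) | 2 + (16/6 − 1)/2 = 2.83 | 70.8% | 4/3 = 1.33 |

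Unpredictable allocation would give 50%. Over 47 blocks of 16, this is about 47 × 10.05 = 472 correct guesses out of 752, against 376 by chance, and about 47 × 1.78 = 84 determined places. These are ceilings under perfect tracking.

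**The case against.** **Reveal on entry.** The Randomisation section can be read as a list that shows the arm only once the child has been entered, and a separate working instruction might lock it. A reader might infer that allocation is simply unconcealed, but the text does not establish that. It describes neither a lock nor an open sheet, so "not reliably concealed" is as far as it goes.

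**The seed.** A reader might infer that anyone can regenerate all 47 lists and predict every allocation. That is not shown. The protocol gives no R version, no exact call and no map from block number to group type, and age group follows demand. Outsiders also do not control consent, and facilitators already hold the list. The seed rule is therefore secondary.

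**Outcome scoring.** A reader might take it that facilitators score the outcome. They read out the items and record the answers. A blinded member of the evaluation team computes the total.

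**Other monitoring.** The date check is not the only safeguard. The delivery organisation is asked to report who does and does not agree to take part (Participants). Baseline characteristics from referral and triage may be adjusted for (Exploratory analysis). Table 4 asks whether randomisation followed the protocol, and both review meetings cover consent and randomisation. Selection on measured characteristics could therefore show. Selection on unmeasured ones would not, and Table 4's evidence on randomisation fidelity comes from staff interviews and manager feedback.

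**Limited discretion.** Triage arranges the first consent call and does the risk assessment. The protocol does not say that the facilitator alone decides when an undecided parent is called again.

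**The guessing figures.** They assume one person sees and tracks every allocation in a block, and the number of facilitators sharing a list is not stated. The 71% matters only when places 17 to 20 are used, and most blocks are expected to hold 16. The sub-blocks have a stated purpose, which is balance when those last places stay empty.

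**It is a pilot.** The protocol says robust estimates are not its focus. But it tests at 0.05, seeks preliminary effect evidence and must recommend a randomisation approach for a full-scale trial. Concealment is part of what the pilot should test.

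**Conclusion.** The point stands in this form. The recruiting facilitator holds the list, and the stated barrier to foreknowledge is an instruction with training, so concealment is not assured. The seed rule adds an avoidable exposure. The order check uses two orderings that diverge whenever a second consent call is needed.

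The size of any selection bias cannot be derived from the document. It depends on whether facilitators look ahead and act on what they see, and nothing in the protocol says that they do. The only calculable quantity is the ceiling from the fixed sub-blocks: about 63% and 71% correct guesses, with about 1.8 of 16 places determined.

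**What to change.** For blocks not yet filled:

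1. Regenerate the lists with undisclosed random seeds, archived and released after recruitment. Reproducibility is kept.
2. Keep the lists with the evaluator, behind a locked form or sheet that releases one allocation only after child ID and consent time are recorded. The facilitator can still tell the parent the arm during the call.
3. Define place order as order of recorded consent, and audit against that timestamp. Remove the competing reference to order of referral.
4. State in the protocol that the fixed 8-of-16 and 2-of-4 sub-blocks leave the predictability shown above for anyone who tracks every past allocation, and that steps 1 to 3 do not remove it.

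The cost is setting up one form or locked sheet and a short amendment. The protocol gives no costing, so calling this small is a judgement. The Iterative testing section already provides for posted amendments and says changes can in principle be made at any point. If no unfilled blocks remain, report the limitation and carry steps 1 to 3 into the recommendation for the full-scale trial.
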